5.2.3 Duration of Overall Response (Biochemical Response)

5.2.3.1 The duration of overall response is measured from the time measurement criteria are met for CR or PR (whichever status is recorded first) until the first date that recurrence or PD is objectively documented.

5.2.4 Reporting of Results

5.2.4.1 All patients included in the study must be assessed for response to treatment, even if there are major protocol treatment deviations or if they are ineligible. Each patient will be assigned one of the following categories: (1) complete response, (2) partial response, (3) stable disease, (4) progressive disease, (5) early death from malignant disease, (6) early death from toxicity, (7) early death because of other cause, or (8) unknown (not assessable, insufficient data).

5.2.4.2 All of the patients who met the eligibility criteria will be included in the main analysis of the response rate. Patients in response categories 4–9 will be considered as failing to respond to treatment (disease progression). Thus an incorrect treatment schedule or drug administration does not result in exclusion from the analysis of the response rate. Precise definitions for categories 4–9 will be protocol specific.

5.2.4.3 All conclusions should be based on all eligible patients.

5.2.4.4 Sub analyses may then be performed on the basis of a subset of patients, excluding those for whom major protocol deviations have been identified (e.g., early death due to other reasons, early discontinuation of treatment, major protocol deviations, etc.). However, these sub analyses may not serve as the basis for drawing conclusions concerning treatment efficacy, and the reasons for excluding patients from the analysis should be clearly reported.

5.2.4.5 The 95% confidence intervals should be provided.

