Early stopping Rule- Should 2 patients in the first 10 patients enrolled on both arms of the trial exhibit a grade 4 toxicity of any type, regardless of the number of patients enrolled (from 2 to 10), then the trial will be temporarily closed to accrual to reevaluate the use of the agents in this combination. The exact upper 90% confidence bound about 2/10 is 45%, while that about 1/10 is 34%. Thus, while 1/10 is marginally consistent with one third of the patients having toxicity, 2/10 is consistent with more than this amount; thus 2 patients with toxicity early in the study are more than would be tolerated in a phase II study of this type.

Those patients who experience a PSA progression while on their initial, randomized therapy will stop flutamide treatment when this is determined. If they were randomized to receive vaccine + flutamide, they will begin to receive vaccine (alone), and if randomized to flutamide alone, they will start vaccine alone instead. The time to development of metastatic disease from the date of discontinuation of flutamide will be evaluated as a secondary endpoint for each arm, using Kaplan-Meier curves. Descriptive analyses of the pattern of change in PSA over time will also be performed.

It is expected that approximately 20-25 patients per year may be enrolled onto this trial. Thus, in order to obtain 66 evaluable patients, accrual of approximately three years will be expected. In order to allow for a very small number of patients who are inevaluable early after enrollment, the accrual ceiling will be set at 70 patients.

Following amendment F, the study will be continue to be randomized in a 1:1 fashion, and will enroll 31 eligible patients on each of the two arms (62 total), in order to have 80% power to detect a difference between a hypothesized median TTF of 10.0 months on flutamide alone and an increase of 8 months, to 18.0 months, with flutamide + vaccine, using a one-tailed 0.1 alpha level test. This difference assumes that patients enrolled on the study will be equally divided between those who have progressed on combined androgen therapy as well as those who have just begun combined androgen therapy. This calculation was made using nQuery Advisor version 5, assuming 60 months accrual, an additional 24 months of follow-up for the last patient enrolled, and hazards of 0.0693 per month for flutamide alone and 0.0385 for flutamide and vaccine, with a resulting hazard ratio of 1.80.

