Following amendment F, patients will be stratified by combined androgen therapy status (progressed; beginning) as well as projected PSA doubling time (≤ 10 vs. > 10 months).

As of the date of Amendment F, 13 patients have enrolled onto the study in approximately 2 years. In order to accrue a total of 62 patients in 5 years, the remaining 49 patients would need to be accrued in 3 years, or approximately 16-18 patients per year. In order to allow for a small number of inevaluable patients, the accrual ceiling will be set at 65.

Following Amendment K, only the patients at NCI will receive sargramostim (GM-CSF). Given the relatively small amount of patients which remain on the trial, descriptive and exploratory analysis will be done comparing patients who received GM-CSF and those who did not.

Following Amendment P, patients at NCI will not receive sargramostim injections. There has not been found to be definitive benefit of the Sargramostim injections to this point. Other studies using the RF-PSA TRICOM are not currently using Sargramostim injections; and the subjects in the multicenter sites are also not required to take/give Sargramostim.

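### Between-arm conclusions rest on eligible rather than all randomised patients, and no analysis population is named for the primary comparison of time to treatment failure

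*Combined protocol and SAP*

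**What the plan says.** Section 5.2.4 carries the only rules on which patients count.

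- 5.2.4.1 asks for response assessment in ineligible patients too (the last word of its sentence, cut here, names them): "All patients included in the study must be assessed for response to treatment, even if there are major protocol treatment deviations or if they are".
- 5.2.4.2 then narrows the set: "All of the patients who met the eligibility criteria will be included in the main analysis of the response rate".
- 5.2.4.3 is general and not confined to response rate: "All conclusions should be based on all eligible patients".

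The same section also protects eligible patients. On treatment deviations, 5.2.4.2 says "Thus an incorrect treatment schedule or drug administration does not result in exclusion from the analysis of the response rate". On outcomes that cannot be assessed, it says "Patients in response categories 4–9 will be considered as failing to respond to treatment (disease progression"), and category 8 is the unknown or unassessable group. Section 5.2.4.4 bars analyses that exclude deviations or early discontinuations from supporting efficacy conclusions.

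Section 5.4 makes TTF the primary endpoint, with failure defined as rising PSA, metastasis, or removal for excessive toxicity. It specifies Kaplan-Meier plots and a log-rank test. It gives neither an analysis population nor a time origin. After amendment F the trial "will enroll 31 eligible patients on each of the two arms (62 total"), and the allowance reads "In order to allow for a small number of inevaluable patients, the accrual ceiling will be set at 65". The superseded sizing counted the same 66 patients first as eligible (33 per arm) and then as evaluable ("in order to obtain 66 evaluable patients"), with a ceiling of 70. Neither evaluable nor inevaluable is defined.

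**The concern.** Randomisation protects a comparison only if everyone randomised stays in it. Read literally, 5.2.4.3 removes a randomised patient who is later judged ineligible, even if his failure has been recorded. Section 5.4 accrues around inevaluable patients without saying who they are, when that is decided, or whether they leave the TTF analysis. This sits uneasily with 5.2.4.2, where an eligible patient who cannot be assessed counts as a response failure.

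The arms may not be equally exposed. Section 3.1 describes an injected vaccine in Arm B only, with no placebo or blinding. Several exclusions in section 2.1.2 bear mainly on vaccine recipients: prior reaction to vaccinia, skin conditions or vulnerable household contacts, and egg hypersensitivity. A missed criterion of this kind is more likely to surface when vaccine is due. Section 5.5 has participating sites send the eligibility checklist for central review within 3 business days. Nothing requires that review to be finished before randomisation or to be blind to arm.

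With about 31 patients per arm, a few selective exclusions would be enough to shift the result of a test at one-sided 0.10.

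**Working it through.** **Inputs (section 5.4, after amendment F).** Median TTF 10.0 v 18.0 months; hazards 0.0693 and 0.0385 per month; hazard ratio 1.80 (flutamide over combination); one-sided alpha 0.10; power 80%; accrual 60 months plus 24 months of follow-up; 31 per arm; ceiling 65.

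**1. Reproduce the plan's sample size.** With exponential times and uniform accrual, the event probability is 1 − [exp(−λF) − exp(−λ(A+F))]/(λA), with A = 60 and F = 24.

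- Flutamide: 0.955. Combination: 0.845. Mean 0.900.
- Expected events from 62 patients: 31 × (0.955 + 0.845) = 55.8.
- Freedman: (1.282 + 0.842)² × (2.80/0.80)² = 55.2, so 56 events; 56/0.900 = 62.2 patients.
- Lachin-Foulkes: 30.9 per arm, rounded to 31.

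The stated 62 is reproduced.

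**2. Room in the ceiling.** (65 − 62)/65 = 4.6%, so three patients can be set aside with 62 still remaining. This is an accrual allowance; the plan does not cap exclusions at three.

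**3. Are three early failures possible?** At 0.0693 per month, 1 − exp(−0.0693 × 3) = 18.8% fail by month 3, or about 6 of 33. Three is numerically possible.

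**4. Effect of exclusions with no treatment effect.** Assumptions: 32 patients in Arm A and 33 in Arm B, median 10 months in both arms, log-rank test at one-sided 0.10, 8,000 simulated trials per row, Monte Carlo error about 0.3 to 0.5 points. The documents do not say how many patients would be excluded or from which arm, so each row is an assumed scenario.

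| Patients removed | One-sided type I error |
|---|---|
| None (all 65 analysed) | 10.7% |
| 3 from Arm B at random | 10.2% |
| 1, 2 or 3 from Arm B who failed within 3 months | 12.9%, 15.2%, 18.8% |
| 3 earliest times in Arm B (worst case) | 19.1% |
| 3 from Arm A who failed within 3 months | 5.6% |
| 3 earliest times in Arm A | 5.7% |

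In the worst case the average null hazard ratio moves from 1.00 to 1.10.

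**5. Effect when the vaccine works as hypothesised.** With a true hazard ratio of 1.80, losing three early failures gives an apparent ratio of about 1.99 to 2.02 if they come from Arm B, and about 1.64 to 1.66 if they come from Arm A.

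**6. Power if everyone is analysed.** Schoenfeld power is Φ(½√d × ln 1.80 − 1.282).

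- 62 patients, d = 55.8: 82.0%.
- 65 patients, d = 65 × 0.900 = 58.5: 83.3% (82.3% by simulation).

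**The case against.** The strongest reply is that section 5.2.4 already closes most of the gap. It counts eligible patients who cannot be assessed as response failures, keeps those with treatment deviations, and stops deviation-excluding analyses from supporting efficacy conclusions. Removal for toxicity is already a TTF event, so it cannot properly be recoded as missing. Eligibility is a baseline matter, confirmed by checklist before registration (sections 2.3 and 5.1.1). If 5.2.4 governs TTF, these safeguards come with it; if it does not, 5.2.4.3 is not the TTF rule either.

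Much of this stands. A reader might infer that conclusions are confined to evaluable patients and that patients lost after randomisation are replaced. The documents say neither: 5.2.4.3 says eligible, and replacement could only be guessed from the ceilings. A reader might also take 19% as the expected error rate, but it comes from deleting three early Arm B failures by construction. With 33 patients and a 10-month median, the three earliest exponential times average about 0.4, 0.9 and 1.4 months. Section 5.2.2.2 first judges PSA progression at week 12, so the simulated timing is stylised. Censoring has limits too: a patient censored before the first event adds nothing to a log-rank test, much as if he were excluded.

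The reply leaves a gap. A patient with a recorded failure is evaluable but can still be found ineligible, and 5.2.4.3 would then remove his event. The safeguards in 5.2.4.2 are written for response rate and for eligible patients. If 5.2.4 does not govern TTF, the primary comparison has no stated population at all.

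**Conclusion.** The concern holds as a defect in specification that carries a risk of bias. The plan bases conclusions on eligible patients, names no population for the primary TTF test, leaves inevaluable undefined, and nowhere calls for analysis as randomised. That the trial is unblinded is read from the arm descriptions, not from an explicit statement.

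Neither the size nor the direction of any bias is established. For three exclusions, type I error runs from about 6% to about 19% depending on which patients go, and stays near 10% if exclusion is unrelated to arm and outcome. Exclusions judged only on pre-randomisation facts, without knowledge of arm or outcome, would do little harm, but the plan does not require this. The figures assume exponential times, 65 patients randomised and at most three removed. The documents give 65 only as a ceiling, so they do not show that 65 were enrolled. The trial's pilot purpose makes the matter less grave, but the correction is inexpensive and worth making.

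**What to change.** - **Section 5.4:** state that the primary TTF analysis includes every randomised patient in the assigned arm, timed from randomisation. Removal for toxicity counts as an event, as already defined, and patients without an event are censored at their last assessment.
- **Section 5.2.4.3:** for between-arm conclusions, replace eligible with randomised patients.
- **Sensitivity analysis:** keep the eligible-only comparison in this role.
- **Reporting:** define inevaluable, reconcile it with 5.2.4.2, and list ineligible or inevaluable patients by arm with reasons.

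The cost is mainly wording. Section 5.2.4.1 already requires ineligible patients to be assessed for response; their TTF data should be kept as well. No increase in sample size is needed. The downside is slight dilution of the effect by patients who were ineligible or barely treated.

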5.2.5 Assay for Immunologic Response

In order to evaluate the potency of clinical vaccines, assays that determine an antigen-specific T lymphocyte response to vaccines have been employed. The ELISPOT assay for IFN production (see **APPENDIX E**) has shown correlation with the results of the CTL assay.(55, 56) The CTL assay has been used successfully in numerous vaccine trials. The ability to detect single cells that produce interferon gamma has led to specificities of 80-95%. Schmittel et al. have shown that the ELISPOT has very good reproducibility both when the same sample is tested at two time points and when an individual is tested at different time points.(57) We have also seen minimal variation in

the flu-specific ELISPOT in patients when tested at time points about 84 days apart.(58)

The primary immunologic endpoint for evaluating the immune response will be the frequency of interferon gamma-releasing T cells specific to PSA-3A, a HLA-A2 restricted epitope of PSA, as measured by the ELISPOT assay. Only the patients who are HLA-A2 positive will undergo ELISPOT analysis. It is planned that all patients will undergo exploratory analysis of the ability to detect CD4 positive responses using a whole protein PSA assay.

In all patients undergoing apheresis, 5×10^8 to 2×10^9 mononuclear cells will be obtained by a single-access (single venipuncture) “four-pass” mononuclear cell procedure on the Haemonetics V-50 instrument, during which 2.0 liters of whole blood would be processed at a flow rate of about 70-80 ml/min. The total duration of the procedure is 90 min to 2 hours. Patients will be required to have a minimum HCT of 28% and a platelet count of at least 75,000 to undergo a Haemonetics procedure. Apheresis will be requested for immunologic testing in patients receiving vaccine at baseline and around weeks 12, 24, and 36(see section 3.4.6).

Anti-PSA antibodies will be measured prior to and following vaccinations using an ELISA assay as previously described ((17)). In addition, tests for anti-vaccinia antibody, anti-fowlpox antibody, anti-GM-CSF antibody, anti-B7.1 antibody, anti-ICAM-1 antibody and anti-LFA-3 antibody will be run in selected patients as previously described. ((35))

As of amendment P, sargramostim (GM-CSF) will no longer be given to patients enrolled at the NCI site because there has not been found to be definitive benefit of the Sargramostim injections to this point. Other studies using the RF-PSA TRICOM are not currently using Sargramostim injections; the subjects in the multicenter sites are also not required to take/give Sargramostim. Thus, with amendment P, tests for anti-GM-CSF antibody will no longer be performed.

5.3 Toxicity Criteria

Common Terminology Criteria for Adverse Events, Version 4.0(CTCAE)

This study will utilize the CTCAE version 4.0 for toxicity and adverse drug experience reporting beginning January 1, 2011. A copy of the CTCAE version 4.0 will be available from the CTEP webpage, <http://ctep.cancer.gov/reporting/ctc.html>. All appropriate treatment areas will have access to a copy of the CTCAE version 4.0.

Toxicity Grading for Vaccinia Toxicity((11)) (see Section 8.2)

Grade 1: Cutaneous reaction extending no more than 10 cm from the vaccination site (i.e., limited to the upper arm).

Grade 2: Any autoinoculation syndrome that resolves without sequelae; Generalized vaccinia extending more than 10 cm from the vaccination site.

Grade 3: Any toxicity that is between grade 2 and 4.

Grade 4: Autoinoculation syndrome (e.g. blindness); post vaccinia encephalitis; vaccinia gangrenosum; eczema gangrenosum; Stevens-Johnson syndrome.

Dose Limiting Toxicities for Flutamide include Grade 4 diarrhea, Grade 4 hepatic toxicity, both which would require discontinuation of the drug. Patients with grade 3 non-autoimmune toxicity due to Flutamide, may resume treatment provided that the toxicity has decreased to baseline or grade 1 toxicity within 42 days of scheduled re-treatment. However, patients with recurrent Grade 3 toxicities will be taken off drug. Grade 4 toxicity would require coming off study.

5.4 Statistical Considerations

The primary objective of this randomized trial is to determine if use of a combination of vaccine plus flutamide may be associated with a trend toward improvement in time to treatment failure in patients with stage D0.5 prostate cancer compared to that which would occur with flutamide alone.

Secondary objectives are 1) determining preliminary evidence of any patterns of immunologic effects which differ by treatment including the immunologic effects of flutamide withdrawal on patients continuing on vaccine following a rising PSA on flutamide, 2) estimating toxicity noted on the arms and comparing the results, 3) evaluating, in a preliminary fashion, the effect of vaccine on development of metastatic disease after PSA progression, and 4) evaluating PSA responses and immune responses in patients who have had flutamide stopped at the time of PSA progression and either continue vaccine (Arm B) or have vaccine initiated (arm A) at time of flutamide discontinuation

The trial will be conducted as a randomized pilot trial with two arms as follows:

Arm A: flutamide

Arm B: flutamide + vaccine

Patients will be stratified based on a projected PSA doubling time (PSADT) of > 10 months vs. ≤ 10 months using the last 2 PSA values 1 month apart prior to enrollment on study.

$$\text{PSADT} = \frac{\log(2) \times t}{\log(\text{final PSA}) - \log(\text{initial PSA})}$$

t=time from initial to final PSA determination

$$\log(2) = 0.301$$

Time to treatment failure (TTF) will be the primary endpoint of this trial, where a treatment failure would be defined as a rising PSA (Bublely Criteria, JCO, 1999), development of metastatic disease, or removal from treatment due to excessive toxicity. Because PSA will be measured monthly and metastatic disease will be evaluated every 3 months, this will be sufficiently frequent for the primary evaluation to be made using standard actuarial methods (Kaplan-Meier plots with a log-rank p-value determinations).

The previously published trial of Nilutamide in a similarly eligible population of patients (stage

D0.5 prostate cancer) conducted at the NCI (protocol 00-C-0137) identified a 7.6 month median time to treatment failure, using the definition above. In the current trial, Flutamide will be used instead of Nilutamide because it has a potentially more favorable toxicity profile. The objective will be to determine, in the context of a randomized phase 2.5 trial, if the addition of vaccine to flutamide alone may be associated with an improvement in time to treatment failure.

The study will be randomized in a 1:1 fashion, and will enroll 33 eligible patients on each of the two arms (66 total), in order to have 80% power to detect a difference between a hypothesized median TTF of 7.6 months on flutamide alone and an increase of 6 months, to 13.6 months, with flutamide + vaccine, using a one-tailed 0.1 alpha level test. This calculation was made using nQuery Advisor version 5, assuming 36 months accrual, an additional 12 months of follow-up for the last patient enrolled, and hazards of 0.0912 per month for flutamide alone and 0.0510 for flutamide and vaccine, with a resulting hazard ratio of 1.788.

The ELISPOT assay will be performed in HLA-A2 patients. The log changes in precursor T cell frequency from pre-treatment to that after 3, 6, and 9 months of therapy will be determined and evaluated for statistical significance, both within an arm and between arms. Since this assay will only be available on a subset of patients, the power to detect differences is unknown and may be limited, and the results will be considered secondary, exploratory and possibly biased. The results will be carefully reported with necessary caveats. In addition, since there is no evidence at this time that HLA-A2 patients will have a significantly different time to treatment failure than those with other HLA types, this parameter will not be used to stratify the randomization.

Toxicity evaluations will take place during each cycle of therapy and worst grades of toxicity, by type, will be compared in a secondary analysis between the study arms.

Early stopping Rule- Should 2 patients in the first 10 patients enrolled on both arms of the trial exhibit a grade 4 toxicity of any type, regardless of the number of patients enrolled (from 2 to 10), then the trial will be temporarily closed to accrual to reevaluate the use of the agents in this combination. The exact upper 90% confidence bound about 2/10 is 45%, while that about 1/10 is 34%. Thus, while 1/10 is marginally consistent with one third of the patients having toxicity, 2/10 is consistent with more than this amount; thus 2 patients with toxicity early in the study are more than would be tolerated in a phase II study of this type.

Those patients who experience a PSA progression while on their initial, randomized therapy will stop flutamide treatment when this is determined. If they were randomized to receive vaccine + flutamide, they will begin to receive vaccine (alone), and if randomized to flutamide alone, they will start vaccine alone instead. The time to development of metastatic disease from the date of discontinuation of flutamide will be evaluated as a secondary endpoint for each arm, using Kaplan-Meier curves. Descriptive analyses of the pattern of change in PSA over time will also be performed.

It is expected that approximately 20-25 patients per year may be enrolled onto this trial. Thus, in order to obtain 66 evaluable patients, accrual of approximately three years will be expected. In order to allow for a very small number of patients who are inevaluable early after enrollment, the accrual ceiling will be set at 70 patients.

Following amendment F, the study will be continue to be randomized in a 1:1 fashion, and will enroll 31 eligible patients on each of the two arms (62 total), in order to have 80% power to detect a difference between a hypothesized median TTF of 10.0 months on flutamide alone and an increase of 8 months, to 18.0 months, with flutamide + vaccine, using a one-tailed 0.1 alpha level test. This difference assumes that patients enrolled on the study will be equally divided between those who have progressed on combined androgen therapy as well as those who have just begun combined androgen therapy. This calculation was made using nQuery Advisor version 5, assuming 60 months accrual, an additional 24 months of follow-up for the last patient enrolled, and hazards of 0.0693 per month for flutamide alone and 0.0385 for flutamide and vaccine, with a resulting hazard ratio of 1.80.

Following amendment F, patients will be stratified by combined androgen therapy status (progressed; beginning) as well as projected PSA doubling time (≤ 10 vs. > 10 months).

As of the date of Amendment F, 13 patients have enrolled onto the study in approximately 2 years. In order to accrue a total of 62 patients in 5 years, the remaining 49 patients would need to be accrued in 3 years, or approximately 16-18 patients per year. In order to allow for a small number of inevaluable patients, the accrual ceiling will be set at 65.

Following Amendment K, only the patients at NCI will receive sargramostim (GM-CSF). Given the relatively small amount of patients which remain on the trial, descriptive and exploratory analysis will be done comparing patients who received GM-CSF and those who did not.

Following Amendment P, patients at NCI will not receive sargramostim injections. There has not been found to be definitive benefit of the Sargramostim injections to this point. Other studies using the RF-PSA TRICOM are not currently using Sargramostim injections; and the subjects in the multicenter sites are also not required to take/give Sargramostim.

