1.2.5 PSA Doubling Time (PSADT)

D'amico et al. have demonstrated that the change in the PSA level during the year before diagnosis has been suggested to be significantly associated with Prostate cancer specific mortality. Following radiation therapy, Prostate cancer specific death and all cause death following PSA failure were noted for patients with a short PSA DT (ie 12 months or less) ((60)). Lee et al. reviewed the medical records of 621 men with nonmetastatic prostate cancer treated with radiation therapy and hormone therapy between 1989 and 2003. Only hormone therapy duration ($p = 0.008$) and PSADT ≤ 8 months (<0.001) were significantly associated with time to true clinical failure. The estimated 5-year rate of any clinical failure was 9.4% for men with a PSADT >8 months and 60.4% for men with a PSA doubling time ≤ 8 months ($p < 0.001$) ((61)). Therefore, based on various reports using a PSADT of greater than 12 months or 8 months as a good prognostic indicator, we plan to stratify using greater than 10 months vs. 10 months or less to differentiate patients who are at a greater risk of disease progression in our proposed study.

1.2.6 Rationale for treating castrate-resistant, non-metastatic prostate cancer patients.

This study is based on a previous study employing an earlier version of a vector-based vaccine targeting PSA and the anti-androgen nilutamide. The results of that study suggested that the combination of anti-androgen and vaccine could improve time to progression and overall survival. ((64);(65)). This previous trial did not require patients to have been treated with a previous anti-androgen prior to enrollment. In addition, a similar proportion of the patients who had no previous anti-androgen had a sustained response as those who had progressed on anti-androgen ((64)). The premise that hormonal therapy will enhance immune response as previously outlined (Section 1.2.4) remains valid, regardless of whether patients have progressed on a previous anti-androgen or not.

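### Section 5.4 does not say whether the primary log-rank test uses the two randomisation strata; specifying a stratified test would recover part of the power lost if those strata are prognostic

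*Combined protocol and SAP*

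**What the plan says.** All of the following is in the combined protocol and SAP.

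- **Strata.** Section 5.4 first names one factor: "Patients will be stratified based on a projected PSA doubling time (PSADT"), cut at 10 months. After Amendment F, "patients will be stratified by combined androgen therapy status (progressed; beginning) as well as projected PSA doubling time". That makes four cells.
- **Primary test.** Section 5.4 says that monthly PSA and three-monthly imaging are frequent enough for "standard actuarial methods (Kaplan-Meier plots with a log-rank p-value determinations". It mentions no stratified log-rank, no adjusted or stratified Cox model, and no other use of either factor. The Amendment F text changes the sample size and the strata but not the description of the test.
- **Sizing after Amendment F.** Section 5.4 plans 31 patients per arm for 80% power at a one-sided level of 0.10. The effect sought is stated as "hypothesized median TTF of 10.0 months on flutamide alone and an increase of 8 months, to 18.0 months, with flutamide + vaccine". Accrual is 60 months with 24 further months of follow-up. The hazards are 0.0693 and 0.0385 per month, a ratio of 1.80. The medians assume patients "equally divided between those who have progressed on combined androgen therapy as well as those who have just begun combined androgen therapy".
- **Reason for the PSADT factor.** Section 1.2.5 cites five-year clinical failure of "9.4% for men with a PSADT >8 months and 60.4% for men with a PSA doubling time" of 8 months or less, and chooses the 10-month cut to separate patients at greater risk of progression.

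**The concern.** The plan stratifies on factors it expects to matter for outcome, and then describes a primary test that makes no use of them. Its own reasoning points to prognosis as the criterion for stratifying. Section 1.2.5 justifies the PSADT cut by risk of progression. Section 5.4 declines to stratify on HLA-A2 because there is no evidence that it affects time to treatment failure. Amendment F raised the control median from 7.6 to 10.0 months alongside the assumed even mix of combined androgen therapy status, yet the power calculation still uses one constant hazard per arm. The mix enters only through the medians.

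When randomisation balances prognostic strata between arms, a log-rank test that omits them uses a variance that is too large and compares two mixtures whose overall hazard ratio is pulled towards 1. Its actual type I error then falls below the nominal 0.10, and power falls with it. At stake is the only powered comparison in a 62-patient trial. The silence also leaves open which of two defensible tests is primary, and with few patients the two could fall on opposite sides of one-sided 0.10.

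**Working it through.** **1. The plan's own figure (section 5.4, Amendment F inputs).** With exponential times and uniform accrual A = 60 and follow-up F = 24, the event probability is 1 − [exp(−λF) − exp(−λ(A+F))]/(λA).

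- λ = 0.0693: 1 − (0.1895 − 0.0030)/4.158 = 0.955
- λ = 0.0385: 1 − (0.3969 − 0.0394)/2.31 = 0.845
- Expected events: 31 × (0.955 + 0.845) = 55.8

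Power at one-sided 0.10 (z = 1.2816):

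- Schoenfeld: Φ(√55.8/2 × ln 1.80 − 1.2816) = Φ(0.914) = 82.0%
- Freedman: Φ(√55.8 × 0.80/2.80 − 1.2816) = Φ(0.853) = 80.3%
- Lachin-Foulkes: 80.1%

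The stated 80% therefore reproduces for a homogeneous population.

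**2. How prognostic might the factors be?** The documents give no hazard ratio (HR) for either factor on time to treatment failure. An indicative value for combined androgen therapy status takes 7.6 months as the median in progressed patients and solves 0.5 × 2^(−10/7.6) + 0.5 × 2^(−10/m) = 0.5. This gives m = 13.5 months and an HR of 13.49/7.6 = 1.78. For PSADT a range of 1 to 3 is assumed.

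**3. Simulation.** Assumptions: 62 patients, each factor split 50:50, permuted blocks of 4 within the four cells, within-stratum treatment HR 1.80, overall control median 10.0 months, 60 + 24 months, 40,000 runs per row. Dividing every stratum hazard by 1.8 stretches time by 1.8, so the overall vaccine-arm median is 18.0 months, as the plan assumes.

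| Prognostic HR (androgen therapy status, PSADT) | Type I error, unstratified | Power, unstratified | Power, four-cell stratified |
|---|---|---|---|
| 1, 1 | 0.104 | 81.2% | 78.2% |
| 1.5, 1.5 | 0.096 | 78.1% | 77.6% |
| 1.78, 1 | 0.096 | 78.4% | 77.8% |
| 1.78, 1.5 | 0.091 | 77.2% | 77.7% |
| 1.78, 2 | 0.084 | 74.1% | 77.2% |
| 2, 2 | 0.084 | 73.6% | 77.5% |
| 1.78, 3 | 0.077 | 68.5% | 76.3% |
| 3, 3 | 0.065 | 63.4% | 75.9% |

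The stratified test holds its type I error at 0.100 to 0.103. Repeat runs move the power figures by about a point.

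**4. Sensitivity (12,000 runs per scenario).**

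- *First 13 patients stratified on PSADT only.* Unstratified power is 78%, 74% and 64% at (1.5, 1.5), (1.78, 2) and (3, 3), so little changes.
- *Allocation not balanced within strata.* Unstratified type I error is 0.100 to 0.105, so the conservatism disappears. Power is still lost: at (1.78, 2) it is 72.3% unstratified and 75.2% stratified.
- *Stratifying the test on PSADT alone.* Power is 79.8% at (1, 1), 76.9% at (1.78, 2) and 76.3% at (1.78, 3). At (3, 3) it is only 68.6%.
- *Cox model adjusted for both factors.* Power is 78% to 81%, with type I error 0.103 to 0.112, slightly above nominal.

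**The case against.** Several stronger readings are tempting, and the case against them is good.

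- **That the plan chose an unstratified test.** It did not say so. The text is silent, and a stratified log-rank is still a log-rank. The sentence is mainly about whether assessments are frequent enough. This stands, but silence does not settle which test is primary.
- **That the 80% is wrong.** It reproduces from the plan's own inputs. The shortfall arises only if the population is heterogeneous in the way the strata suggest.
- **That section 1.2.5 proves a very strong PSADT effect.** The cited rates imply ln(1 − 0.604)/ln(1 − 0.094) = 9.4, and at that value unstratified power would be about 45%. But those rates are for clinical failure after radiation and hormone therapy, at an 8-month cut. The trial uses a PSADT projected from two values one month apart, a 10-month cut, and an endpoint that includes PSA rise. The figure cannot be carried over.
- **That combined androgen therapy status is known to be prognostic.** The 1.78 is back-solved. Section 1.2.6 says the 7.6-month cohort included patients who had not progressed on earlier anti-androgens.
- **That stratifying repairs the power.** In every scenario the four-cell test gives 76% to 78%. With no prognostic effect it loses about 3 points. The gain also depends on the PSADT split: with 90% of patients in one group and a PSADT HR of 3, it is about 4 points (74% to 78%).
- **That the type I error is compromised.** A conservative test is valid and does not favour a false positive. The effect also needs balance within strata, and no block method is stated.

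The trial is, in addition, a pilot looking for a trend. These points limit the size and grade of the concern. They do not remove the gap in the specification.

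**Conclusion.** The concern holds in a limited form. Two factors stratify the randomisation, and section 5.4 specifies only a log-rank p-value without using them. If they are prognostic and allocation is balanced within cells, the test without them is conservative and loses power.

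The gain from stratifying the test is nil at an HR of about 1.5 per factor, or with combined androgen therapy status alone. With that status at 1.78, it is about 3 points at a PSADT HR of 2 and 7 to 8 points at 3. The cost is about 3 points if neither factor matters. These figures rest on assumed prognostic HRs, an even split of each factor and blocked allocation, none of which the documents give in full.

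A reader might infer that the sample size is miscalculated, or that a stratified test would deliver 80%. Neither follows. Grade: should-fix, as a cheap improvement to the specification; the trial's validity is not in question.

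**What to change.** In section 5.4, before any comparison of outcome by arm:

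1. Name the primary test as a one-sided 0.10 log-rank stratified by the randomisation factors: PSADT (≤ 10 vs > 10 months) and combined androgen therapy status (progressed vs beginning).
2. Report the hazard ratio from a Cox model stratified in the same way.
3. Keep the unstratified log-rank as a sensitivity analysis.
4. Classify combined androgen therapy status for the 13 patients enrolled before Amendment F from their baseline history.
5. State a rule for sparse cells. Four cells average 31/4, or about 8 patients, per arm. One option is to collapse to PSADT alone when a cell falls below a size fixed in advance. In the scenarios with combined androgen therapy status at 1.78, that version loses almost nothing against the four-cell test, and it costs only about 1.5 points if nothing is prognostic.

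The change is a few sentences and needs no new patients or visits. Its price is the roughly 3 points of power if both factors turn out not to matter. The sample-size paragraph can stand, with a note that its 80% assumes one hazard per arm.
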